9.5.5.2 Electrocardiogram analysis (Part C)

The same analysis to Part A will be performed in Part C, but the change from baseline adjustment will be based on individual subject's Day 1 predose value, and an additional placebo adjustment will be based on mean time-matched placebo values.

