12-lead ECG (hours)	X			Predose (-45 min, -30 min, -15 min)	Predose		Predose		Predose, (-45 min, -30 min, -15 min), 2, 3, 4, 6, 8, 12	24	X	X	Single safety ECGs at screening and ED/follow-up; triplicate ECGs at all other times. ECGs coinciding with PK sample time points are to be conducted as close as possible prior to PK sampling.	
PGx sample				X									Single sample for pharmacogenetic analysis taken prior to/on Day 1.	
Stored non-PGx plasma sample (hours)				Predose, 8			Predose		Predose, 8					
PK sampling (hours)				Predose, 0.5, 1, 2, 3, 4, 5, 6, 8, 12	Predose		Predose, 0.5, 1, 2, 3, 4, 5, 6, 8, 12	Predose (D8 only)	Predose, 0.5, 1, 2, 3, 4, 5, 6, 8, 12	24			Sampling times are relative to the time of LY3154885 administration (0 hour).	
POMS-2®			X			D6 only		D13 only						
Exploratory cognition assessments (HVLT, DSST)			X			D6 only		D13 only						
PWC-20				Predose						X	X	X		
C-SSRS and Lilly Self-Harm Supplement Form	X	X				D3 & D6 only		D8 & D10 only		X	X	X	Administer at screening, each admission, and each discharge from the CRU.	

Note: Site should schedule activities as appropriate. In cases where several study procedures are scheduled at the same time, follow this order of priority for procedures: ECG, vital signs, PK samples, clinical laboratory tests, biomarkers, and storage samples.

Abbreviations: ABPM = ambulatory blood pressure monitoring; AE = adverse event; BP = blood pressure; CRU = clinical research unit; C-SSRS = Columbia-Suicide Severity Rating Scale; D = day; DSST = Digital Symbol Substitution Test; ECG = electrocardiogram; ED = early discontinuation; HVLT = Hopkins Verbal Learning Test; MA = medical assessment; PE = physical examination; PGx = pharmacogenetic; PI = principal investigator; PK = pharmacokinetic; POMS-2 = Profile of Mood States Second Edition; PR = pulse rate; PWC-20 = Penn Physician Withdrawal Checklist.

Study Schedule Protocol J1Z-MC-HUAA (Part D: Formulations/Food Effect – 3 Study Periods)

		Periods 1, 2, and 3																
	Screening	Days														ED	Follow-up	Comments
Procedure	-28 to -3	-2	-1	1	2	3	4-6	7	8	9	10	11-13	14	15	16		Approx 7 days after discharge	
Informed consent	X																	
Admission to CRU		X	X				X D6					X D13						Admission on Day -2 is for Periods 1 and 2. Admission on Day -1 is for Period 3.
Discharge from CRU					X					X					X			
Medical history	X																	
AE/medication review	X		X	X	X	X	X	X	X	X					X	X		
Height/weight	X		X					X							X	X	Height at screening only	

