5.1.3. Part C (Multiple-Ascending Dose)

The decision to conduct Part C will be made after review of safety, tolerability, and PK data from Parts A (SAD) and B (CYP3A4 Inhibition).

[figure not shown]
Part C will explore up to 3 dose levels in 3 separate cohorts (Cohorts 4 to 6) of healthy subjects. Each cohort will consist of approximately 12 subjects (9 LY3154885; 3 placebo) dosed daily for 14 days with a capsule formulation.

Subjects will participate in a single study period consisting of 14 days of once-daily dosing with LY3154885 or placebo; study drug will be administered as a single oral dose in the morning under fasted conditions (see Section 6.3.1). Subjects will be admitted to the CRU on the afternoon of Day -2 for set up of baseline ABPM (see Section 9.4.4) and will be required to remain in-house for at least 48 hours after dosing (Day 3), and at the discretion of the investigator. As detailed in the Schedule of Activities (Section 2), subjects will attend the CRU on Days 4, 5, 6, 9, and 10 on an outpatient basis for daily dosing and will be permitted to leave the CRU at the discretion of the investigator. Pharmacokinetic sampling will be conducted as detailed in Section 2. To assess CV effects and potential accommodation over time, ABPM will

be included on Day -1 (baseline) and on Days 1, 2, 7, 11 and 12, and 14. A poststudy follow-up visit will be conducted approximately 7 days after discharge.

The doses evaluated will be selected based on emerging data from Parts A and B and from the lower doses from Part C (see Section 5.5 for details). If the safety data do not support increasing the dose in subsequent cohorts, then a dose may be repeated or lower/intermediate doses may be explored. The PK data obtained during the study may be used to assist in dose-escalation decisions, but such data are not required for dose-escalation purposes. For the safety review prior to dose decisions between cohorts, all available safety data (AEs, vital signs, ECGs, and laboratory results) to Day 14 from at least 6 subjects taking LY3154885 must be reviewed by the sponsor and investigator. In addition, each cohort (including at least 6 subjects treated with LY3154885) will complete dosing to Day 14 prior to the next cohort being admitted to the CRU for dosing.

Figure HUAA.5.3 illustrates the study design for Part C.

Abbreviations: LY = LY3154885; PL = placebo; QD = once daily.

Figure HUAA.5.3. Illustration of study design for Part C.

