In Part B (CYP3A4 Interaction), the LY3154885 dose selection will be based on emerging data from Part A but is currently planned to be ≤ 200 mg. It is predicted that the maximum exposure increase in LY3154885 when administered with itraconazole, a strong CYP3A4 inhibitor, is

approximately 2.6-fold. Therefore, the LY3154885 dose selected will be below the highest dose deemed well tolerated that has a plasma exposure to allow for up to a 2.6-fold increase in exposure that may result from coadministration with itraconazole, and the predicted LY3154885 plasma exposure at this dose when coadministered with itraconazole will be below 1/10th the AUC at the NOAEL in monkeys and 1/10th the C_{max} at the NOAEL in rats. The dose regimen for itraconazole will be 200 mg twice daily on Day 8 (dose separated by 12 hours) and once daily on Days 9 through 17.

[figure not shown]
In Part C (MAD), the doses will be based on emerging safety, tolerability, and PK data from Part A (SAD) and Part B. Emerging safety and tolerability data from Part C will also be considered for dose escalation. The highest dose tested in Part C will not exceed the highest dose in Part A (currently planned to be 500 mg) that was well tolerated or the maximum exposure achieved in Part A or B found to be well tolerated.

In Part D, the planned dose for the capsule and tablet will be ≤ 400 mg but will ultimately be based on emerging safety, tolerability, and PK data from Part A.

CCI

CCI

6. Study Population

Eligibility of subjects for the study will be based on the results of screening medical history, physical examination, vital signs, clinical laboratory tests, and ECG. The nature of any conditions present at the time of the physical examination and any preexisting conditions will be documented.

Screening may occur up to 28 days prior to enrollment. Subjects who are not enrolled within 28 days of screening may be subjected to an additional medical assessment and/or clinical measurements to confirm their eligibility.

Prospective approval of protocol deviations to recruitment and enrollment criteria, also known as protocol waivers or exemptions, are not permitted.

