9.3.2 Pharmacokinetic Statistical Methodology

Statistical analysis of the PK parameters will be produced by Covance. All summary outputs will be produced by Lilly.

Part A: The PK parameters C_{max} and AUC for LY3154885 will be evaluated to estimate the dose-exposure proportionality of LY3154885 using a linear-mixed-effect power model. In this model, log-transformed dose will be the independent variable and subject will be a random effect. Both C_{max} and AUC will be log-transformed prior to analysis. The least-squares (LS) means for each treatment together with the treatment differences and associated 90% confidence intervals (CIs) will be estimated from the model. These estimates will be back-transformed to present geometric means, the ratios of geometric means, and the corresponding 90% CIs.

Example SAS code for the analysis:

```
proc mixed data=xxx;
  class subject;
  model log_pk = log_dose / alpha=0.1 cl solution outpred=resids ddfm=kr;
  random subject;
  estimate 'xx mg' intercept 1 log_dose yy / alpha=0.1 cl; /*Log value of xx*/
  estimate 'zz mg - xx mg' log_dose pp / alpha=0.1 cl; /*Difference in log
  values of zz and xx*/
  ods output solutionf=est estimates=estims;
run;
```

Part B: The PK parameters C_{max} and AUC for LY3154885 when administered alone and with itraconazole will be compared using an analysis of variance (ANOVA) model. The parameters will be log-transformed prior to analysis. The model will include a fixed-effect for the treatment (LY + itraconazole : LY) and a random effect for subject. The LS means for each treatment, the difference between the treatment LS means (LY3154885 + itraconazole – LY3154885), and the associated 90% CIs will be estimated from the ANOVA model and back-transformed from the log scale to provide estimates of the geometric means, geometric mean ratio, and corresponding 90% CIs.

Example SAS code for the analysis:

```
proc mixed data=xxx;
  class treatment subject;
  model log_pk = treatment / residual ddfm=kr;
  random subject;
  lsmeans treatment / cl pdiff alpha=0.1;
  ods output lsmeans=lsm diff=estims;
run;
```

The t_{max} of LY3154885 for both treatments will be analyzed using a Wilcoxon signed-rank test. An estimate of the median difference and 90% CI will be calculated.

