9.5.5.1 Electrocardiogram analysis (Part A)

The relationship between the time-matched LY3154885 concentrations and changes from baseline and time-matched placebo in QTcF interval will be explored graphically using a scatter plot. A regression analysis using a linear mixed-effects model will be performed. A plasma LY3154885 concentration-QT analysis will be performed to assess the changes from baseline (Day 1 predose) and time-matched mean placebo in the QTcF interval relative to plasma LY3154885 concentrations across all dose levels. The change from baseline adjustment will be based on individual subject's Day 1 predose value, and an additional placebo adjustment will be based on individual subject's time-matched placebo values. The analysis will be performed by plotting double delta QTcF against LY3154885 concentrations, including all post dosing timepoints. A linear mixed-effects model will be performed on the double delta QTcF values and will include LY3154885 concentration as a covariate. The estimated regression line and associated 90% confidence interval (CI) will be fitted on the plot and the p-value for the slope reported. Estimated delta QTcF and 90% CI at the geometric mean C_{max} (estimated from the highest given dose in the study) will also be presented.

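### The Part C concentration-QTcF analysis treats the subtracted placebo mean as known, so its 90% CI is too narrow

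*SAP*

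**What the plan says.** SAP 9.5.5.2 states that "The same analysis to Part A will be performed in Part C", except that "an additional placebo adjustment will be based on mean time-matched placebo values". In Part A (SAP 9.5.5.1) each crossover subject can supply their own placebo values.

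The Part A model is described in one sentence: "A linear mixed-effects model will be performed on the double delta QTcF values and will include LY3154885 concentration as a covariate". From it the SAP reports a regression line with a 90% CI, a p-value for the slope, and an estimate with a 90% CI at the geometric mean Cmax, "estimated from the highest given dose in the study". No random effect, time term or treatment term is named, and no code is given. By contrast, in SAP 9.3.2 the Part A dose-proportionality model says that "log-transformed dose will be the independent variable and subject will be a random effect".

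On numbers, protocol 5.1.3 says: "Each cohort will consist of approximately 12 subjects (9 LY3154885; 3 placebo) dosed daily for" 14 days, in up to three cohorts. The SAP does not say whether the placebo mean is pooled over cohorts or taken within each. Its treatment list (SAP 6) has a single Part C placebo entry, which points to pooling.

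**The concern.** A double delta for an active subject is that subject's change from baseline minus an estimated placebo mean. The same estimate is subtracted from all 27 active subjects, or from the 9 in a cohort. If it is off by 2 ms, all of them move by 2 ms together. A model fitted to active subjects alone cannot tell that shift from a drug effect and gives it no variance. A random subject effect, had one been named, would not help, because the error is common to subjects rather than specific to each.

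Part C is the multiple-dose part and the only one with triplicate ECGs. Its interval will be read as the uncertainty of the placebo-corrected QTcF effect after 14 days of dosing. If it is too narrow, the report claims more assurance than 9 placebo subjects can give.

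Two wording points affect the same estimate:

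- The highest dose in the study may be a Part A single dose above the Part C range, since "The highest dose tested in Part C will not exceed the highest dose in Part A" (protocol 5.5).
- SAP 9.5.5.1 labels the result delta QTcF although the model is for double delta.

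**Working it through.** **Counts.** 3 cohorts x (9 + 3) = 36, which matches the completer target in SAP 7: 27 active and 9 placebo. The plan states no SD, power or CI width for this analysis.

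**Bound that needs no SD.** Take the between-subject part of the variance, equal in both groups, with SD σ.

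- Pooled: reported variance σ²/27; true variance σ²(1/27 + 1/9) = 4σ²/27. Reported/true SE = √(1/4) = 0.50.
- By cohort: reported σ²/9; true σ²(1/9 + 1/3) = 4σ²/9. The ratio is again 0.50.
- Coverage of a nominal 90% CI: 2Φ(1.645 × 0.50) − 1 = 2Φ(0.822) − 1 = 0.59.

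**Full model: inputs from the protocol.** The Part C schedule gives 10 ECG times with matched PK after the first dose: predose on Days 2, 7 and 14, then 2, 3, 4, 6, 8, 12 and 24 h after the Day 14 dose (the Day 14 entry reads "Predose, (-45 min, -30 min, -15 min), 2, 3, 4, 6, 8, 12"). Half-life is about 12 h (3.2) and the planned Part C start is 35 mg (5.5).

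**Inputs assumed.** Between-subject SD of the QTcF change 2, 5 or 8 ms; residual SD 5 or 8 ms; absorption rate 1/h; exposure CV 30%; a random subject intercept. Three dose sets serve only to generate concentrations: 35/70/150, 35/100/300 and 35/150/500 mg. This gives 18 combinations, with 4000 simulated trials each.

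| | At Part C top-dose Cmax | At 500 mg single-dose Cmax |
|---|---|---|
| Coverage, pooled placebo mean | 63-76% | 62-78% |
| Coverage, by-cohort mean | 65-68% | 66-69% |
| Coverage, joint model with placebo records | 90-91% | 89-92% |
| CI width, pooled | 3.1-7.9 ms | 2.4-16.9 ms |
| CI width, joint | 4.6-12.9 ms | 3.9-23.7 ms |
| Shift in upper bound | 0.7-2.7 ms | 0.6-3.4 ms |

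With the variance components taken as known, exact calculation gives 60-74% pooled and 59-62% by cohort over both prediction points. Together these give the overall range of about 59-77%.

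**One case in full.** A separate simulation (600 trials) used 35/100/300 mg with both SDs at 6 ms, at the top-dose Cmax:

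- Pooled: mean reported SE 1.68 ms against an actual 2.97 ms; ratio 1.68/2.97 = 0.57; coverage 65%.
- By cohort: 1.85 against 3.28 ms; ratio 0.56; coverage 65%.
- Joint model: 2.81 against 2.80 ms; coverage 91%.
- Half-width 2.87 ms pooled and 4.76 ms joint, so the upper bound moves about 4.76 − 2.87 = 1.9 ms.

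**Other specifications** (exact variance, both prediction points, both placebo readings):

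- two cohorts only: 59-73%
- no intercept: 60-70%
- added random slope (assumed SD 5 ms at top Cmax): 63-79%
- added fixed nominal-time effect: 60-89%

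With a random subject intercept retained, none reaches 90%. With no random effect at all, which is what the SAP literally names, pooled coverage at the Part C Cmax falls to 39-69%.

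**The case against.** The strongest reply is that the SAP under-specifies this model rather than mis-specifying it. It calls the model mixed without listing random effects, does not say concentration is the only term, and refers to a separate TFL shell document that may say more. Keeping placebo records out of the model is the plain reading, not an explicit statement. All of this is fair, but the SAP should carry the model, and no term it names covers the placebo error.

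A nominal-time term would help. With a pooled mean, the placebo error depends only on time, so that term removes it from the slope, whose coverage returns to 90%. It does not repair the level of the line: in the 6/6 ms case, coverage at Cmax rises only to 78% pooled and 66% by cohort.

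Pooling is the likelier reading, so the by-cohort figures deserve less weight. The conclusion is the same either way.

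The 35/150/500 mg set is a poor illustration. Under the assumed PK, steady-state Cmax at 500 mg once daily is about 1.36 times the single-dose value, which may exceed the exposure cap in protocol 5.5. Leaving that set out barely changes the exact pooled range at the Part C Cmax: 60-72% instead of 60-73%.

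The consequence is limited. The sample size is not powered on a hypothesis test, escalation rests on safety review, and the QTcF discontinuation rule applies subject by subject. SAP 9.5.12 even says no inferential safety analysis is planned, which sits awkwardly with the CI and p-value in 9.5.5.1. This limits the importance of the point, but the interval will still be reported.

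**Conclusion.** The concern holds. As written, the Part C 90% CI omits the sampling error of the placebo mean and is too narrow. The direction follows from the design and the subtraction and does not depend on any assumed SD.

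The size does. The SE ratio of 2.0 is a bound that rests on 3:1 allocation and equal variance in the two groups. Coverage of about 59-77%, or a miss rate of 23-41% instead of 10%, also rests on the assumed SDs, PK, upper doses and random intercept. With a time term the range is 60-89%.

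This should be corrected before analysis. It affects how a safety estimate is reported, not how the trial is conducted. The source of the Cmax and the delta/double-delta label are separate clarifications, best settled in the same edit.

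**What to change.** Replace the model in SAP 9.5.5.2 with a joint one:

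- Response: QTcF change from Day 1 predose, in all LY3154885 and placebo subjects, with placebo concentration set to 0.
- Fixed effects: concentration, treatment (active or placebo), nominal time and baseline QTcF. Random effect: subject.
- Report: treatment effect + slope × geometric mean Cmax, with its model-based 90% CI, labelled as double delta QTcF.
- State which part and dose supply that Cmax, and flag the estimate as an extrapolation if it lies above the concentrations seen in Part C.

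The cost is a paragraph of SAP text and one PROC MIXED call on data already collected. The SAP was written against amendment (a), and amendment (b) changed the Part C ECG times, so this section needs revisiting in any case. The downside is a wider interval: 1.2-1.9 times the pooled-mean method under the assumptions above.

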9.5.6 Ambulatory Blood Pressure Monitoring

Ambulatory blood pressure monitoring (ABPM) will be performed in all parts of the study. A 24 hours baseline (off study drug) will be measure in all subjects and at least a 2 hour measure prior to dose will be also be measured on selected dosing days. The ABPM device will record ambulatory BP and PR every 30 minutes during awake hours (e. g. 0700 hours to 2200 hours) and every 60 minutes throughout the night (e.g. 2200 hours to 0700 hours).

The primary parameters for the ABPM data will be peak hourly mean values of systolic blood pressure (SBP), diastolic blood pressure (DBP), and mean arterial pressure (MAP), and nadir hourly mean values for PR. These data will be listed and summarized by part and treatment.

Mean hourly SBP, DBP, MAP, and PR values will be calculated, summarized by part and treatment, and plotted, together with changes from baseline. Baseline value will be defined as the mean value during the 2 hours prior to the planned dosing time.

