7.4.1. Dose Decision/Escalation

By nature of being a dose-escalation study, data will be evaluated on an ongoing basis until the maximum tolerated dose (MTD) is determined or the highest planned dose is administered. The highest dose level that is tolerated will be designated as the MTD.

Safety data will be the primary criteria for the dose escalation. In addition, if available at the time of the dose-escalation decision, PK results will be used as supporting data. No dose escalation can occur without prior discussion and agreement between the investigator and the Lilly study team. See Sections 5.1.1 and 5.1.3 for further details.

Safety data, in particular AEs, SAEs, BP, PR, and adverse laboratory abnormalities, will be independently assessed by the investigator and will be considered related to the investigational medicinal product, unless there is clear evidence that the event is not related.

If any of the following scenarios occur, dosing at the current level and further dose escalation will be discontinued:

- 1) a single subject experiences an SAE that is related to LY3154885 administration
- 2) 2 subjects experience a clinically significant event of persistent tremors that is deemed to be related to LY3154885 administration
- 3) 2 subjects experience clinically significant increases in scheduled vital signs that are deemed to be related to LY3154885 administration
- 4) 2 or more subjects at 1 dose level experience other moderate or severe treatment-related AEs that impair normal activities and are deemed to be related to LY3154885 administration

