8.2. Discontinuation from the Study

Subjects will be discontinued in the following circumstances:

- Enrollment in any other clinical study involving an investigational product or enrollment in any other type of medical research judged not to be scientifically or medically compatible with this study

- Participation in the study needs to be stopped for medical, safety, regulatory, or other reasons consistent with applicable laws, regulations, and good clinical practice (GCP)
- Investigator Decision
 - the investigator decides that the subject should be discontinued from the study
 - if the subject, for any reason, requires treatment with another therapeutic agent that has been demonstrated to be effective for treatment of the study indication, discontinuation from the study occurs prior to introduction of the new agent
- Subject Decision
 - the subject requests to be withdrawn from the study
- If any of the potentially clinically significant vital sign criteria (Table HUAA.8.1) are met at 3 **consecutive scheduled** time points using in-clinic vital sign monitoring on Day 1 and following study drug dosing, the subject should be discontinued from the study drug. The relative value of the potentially clinically significant vital sign criteria is calculated by comparing the mean of the 3 supine BP and PR measurements at Time 0 on that day.

Table HUAA.8.1. Potentially Clinically Significant Vital Sign Criteria

	Low^a	High^a
Systolic BP (mm Hg)	≤90 AND ≥20 decrease	≥180 AND ≥20 increase
Diastolic BP (mm Hg)	≤50 AND ≥15 decrease	≥105 AND ≥15 increase
Pulse Rate (bpm)	≤50 AND ≥15 decrease	≥120 AND ≥15 increase

Abbreviations: BP = blood pressure, bpm = beats per minute, mm Hg = millimeters of mercury

^a Both conditions on absolute AND relative values are required for the measures to meet the criteria for potentially clinically significant (for example BP ≥180 AND ≥20 increase are both required for systolic blood pressure to meet the criteria for potentially clinically significant)

- For vital sign measurements that meet the criteria for potentially clinically significant vital signs (Table HUAA.8.1), action will be left to the discretion of the investigator and may include discontinuation of study drug or subject. Prior to subject being discontinued from the study, the investigator should consult with the Lilly clinical pharmacologist (CP) or designee.

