9.4.4. Ambulatory Blood Pressure Monitoring

Ambulatory blood pressure monitoring will be performed in all parts of the study. The ABPM device will be fitted to the subject's nondominant arm and will record ambulatory BP and PR every 30 minutes during awake hours (0700 hours to 2200 hours) and every 60 minutes throughout the night (2200 hours to 0700 hours). All Day -1 recordings are 24 hours and will serve as baseline. The recording on dosing days will be initiated approximately 2 hours prior to the planned dosing time (baseline value) and will continue according to the Schedule of Activities (Section 2). Subjects will be encouraged to maintain light activity (e.g, walking) and keep the same routine during the ABPM study days. Ambulatory blood pressure monitoring data may not be used for subject management or dose escalation decisions.

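### The SAP's primary ABPM summary of pulse rate uses only the nadir, so each subject's postdose peak pulse goes unsummarised

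*SAP*

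**What the plan says.** SAP 9.5.6 names the primary ABPM parameters: the peak hourly mean for systolic, diastolic and mean arterial pressure, and "nadir hourly mean values for PR". They are listed and summarised by part and treatment. The section gives no reason for the different direction, and no time window for peak or nadir.

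The same section plans a second summary: "Mean hourly SBP, DBP, MAP, and PR values will be calculated, summarized by part and treatment, and plotted, together with changes from baseline". Baseline is the mean over the 2 hours before planned dosing.

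Protocol 9.4.4 sets half-hourly readings from 07:00 to 22:00 and hourly readings from 22:00 to 07:00. On dosing days recording starts about 2 hours before the dose and then follows the Schedule of Activities. A 24-hour length is stated only for Day -1. ABPM is barred from decisions on managing subjects or escalating the dose. Doses are given in the morning (Protocol 7.1).

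Pulse increases matter elsewhere in the protocol. One scenario that ends escalation in Protocol 7.4.1 is that "2 subjects experience clinically significant increases in scheduled vital signs that are deemed to be related to LY3154885 administration". In Protocol 8.2, the high pulse limb of Table HUAA.8.1 reads "≥120 AND ≥15 increase", and the table is applied "using in-clinic vital sign monitoring on Day 1 and following study drug dosing". It also has a low pulse limb: 50 bpm or less with a fall of at least 15.

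**The concern.** For blood pressure, the primary ABPM parameters look for the highest value in a recording. For pulse they look for the lowest. The escalation scenario on vital signs concerns increases, and Protocol 3.2 and 5.5 describe the nonclinical cardiovascular effects as transient. A transient pulse rise after a morning dose would fall in the daytime. A nadir taken from a recording that includes the night would tend to fall hours later, on a single reading.

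At stake is how pulse effects are reported in a study whose primary objective is safety and tolerability. ABPM is the densest source of pulse data, and in Part C it is there to assess cardiovascular effects and accommodation over time (Protocol 5.1.3). If some subjects have a short rise in pulse, the parameter labelled primary could look the same with and without it.

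**Working it through.** The documents state no figure on this point, so there is none to reproduce. The check counts readings from the schedule and then simulates.

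**1. Readings per hourly mean (Protocol 9.4.4).** Awake: 15 h × 2 = 30 readings. Night: 9 h × 1 = 9 readings. If one reading has SD s, a daytime hourly mean has SD s/√2 and a night one has SD s. For s = 4, 6 and 8 bpm the daytime SDs are 2.8, 4.2 and 5.7 bpm.

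**2. Model.** Hourly mean in hour h = 72 − d × (1 at night, 0 by day) + e(h) + independent normal error with the SDs of step 1. There are 24 hourly means, counted from the dose. Nadir = smallest, peak = largest. Each scenario has 40,000 simulated recordings.

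- From the documents: reading intervals, morning dosing, projected half-life of about 12 h (Protocol 3.2).
- Assumed: dose at 08:00, a 24 h recording, night dip d of 0 to 15 bpm, s of 4 to 8 bpm, a peak drug effect of 20 bpm, and a daytime level of 72 bpm (it cancels in every difference).

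**3. Where the nadir falls without a drug effect** (range over s):

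| Night dip (bpm) | Nadir in a single-reading night hour |
|---|---|
| 0 | 63 to 64% |
| 3 | 82 to 93% |
| 5 | 90 to 99% |
| 8 | 96 to 100% |
| 10 | 99 to 100% |

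Night hours are 9/24 = 37.5% of the day. Even with no dip the nadir favours them, because single readings vary more than two-reading means.

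**4. How far a 20 bpm effect moves each parameter.** Shift = mean with effect − mean without, for dips of 0, 5, 10 and 15 bpm and s = 4, 6 and 8:

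| Time course of effect | Nadir shift (bpm) | Peak shift (bpm) |
|---|---|---|
| Transient, +20 in the hourly means 1 to 6 h postdose | 0.0 to 0.4 | 13.9 to 18.7 |
| Follows concentration, +20 at its highest | 8.6 to 9.6 | 14.0 to 17.8 |
| Constant +20 | 19.9 to 20.0 | 20.0 |

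In the transient case with a dip of 5 bpm or more, the nadir shift is at most 0.1 bpm. The concentration curve is c(t) = exp(−t·ln2/12) − exp(−t·ln2/0.75), taken at mid-hour and scaled to a maximum of 20 bpm; the 0.75 h absorption half-life is assumed. It leaves 7.0 to 11.1 bpm of effect in the night hours.

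The mechanism shows without noise at d = 5. The night level is 72 − 5 = 67. A transient rise takes the peak from 72 to 92 and leaves the nadir at 67. An effect that follows concentration lifts the nadir to 67 + 7.0 = 74.0. A constant rise lifts it to 67 + 20 = 87.

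**5. What the group hourly mean shows.** Active subjects per dose level are 8 in Part A and 9 in Parts B and C. If one subject rises by 20 bpm in a given hour, the group mean for that hour moves by 20/8 = 2.5 or 20/9 = 2.2 bpm.

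**6. Why the window matters.** Step 4 uses postdose hours only, which SAP 9.5.6 does not specify. Recording starts about 2 h before dosing. With an 08:00 dose, the 06:00 hour is a predose hour at the night level of 67 in this model. If it counted, even a constant +20 would leave the noise-free nadir at 67 instead of 87.

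**The case against.** The strongest reply is that pulse increases are already reported in several ways.

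- SAP 9.5.6 itself summarises and plots hourly mean pulse with change from baseline.
- SAP 9.5.4 summarises in-clinic pulse by timepoint with change from baseline and lists individual values. SAP 9.5.5 does the same kind of summary for ECG heart rate.
- SAP 9.1 lists all databased data and includes minimum and maximum in summaries of continuous data. The highest value at each hour should therefore appear.

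All of this stands, and it makes the gap small. What remains is that no summary takes each subject's own peak. The hourly means dilute a rise in a few subjects, or at differing hours. The hourly maxima show the extreme of the group at each hour, but not how subjects' peaks are distributed. For QTcF, SAP 9.5.5 does tabulate each subject's maximum increase; pulse has no counterpart.

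A reader might infer that a nadir-only parameter weakens the stopping rules. The documents do not support that. The escalation scenario refers to scheduled vital signs, Table HUAA.8.1 is applied to in-clinic measurements, and Protocol 9.4.4 keeps ABPM out of these decisions.

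The nadir may also be deliberate. Table HUAA.8.1 has a low pulse limb, and nonclinical text beside the cardiovascular statements is redacted. The missing reason is therefore not held against the plan, and the nadir should stay.

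Finally, the label has limited weight: these are descriptive ABPM parameters, the study's primary endpoint is the incidence of treatment-emergent adverse events, and SAP 9.5.12 plans no inferential safety analysis. That also stands.

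**Conclusion.** The point holds as a reporting gap. If the recording runs overnight and pulse dips by about 5 bpm or more, the primary pulse parameter usually rests on one overnight reading (about 90 to 100% of simulated recordings). It is nearly insensitive to a transient postdose rise: 0 to 0.4 bpm, against about 14 to 19 bpm for the peak.

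Two stronger readings are tempting, and neither is supported:

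- That the nadir cannot show a pulse increase. A constant rise moves it in full, and one that follows a 12 h half-life moves it by about half (8.6 to 9.6 of 20 bpm). Part C doses daily for 14 days, so a sustained effect is possible there.
- That the nadir is almost always a single night reading. With no dip the share is 63 to 64%, and the documents give no dip. An overnight recording is also not certain on every dosing day: in Part C, Days 7 and 14 have no ABPM entry on the following day.

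The percentages and shifts rest on the assumed dip, reading SD, 08:00 dose, 24 h recording and 20 bpm effect. The one-sided choice of parameter and the single night reading per hour come directly from the documents. The change is worth making because it costs very little.

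**What to change.** In SAP 9.5.6:

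- Keep the nadir hourly mean pulse rate.
- Add each subject's postdose peak hourly mean pulse rate and its change from the 2-hour predose baseline, summarised by part and treatment in the same way as the blood pressure peaks.
- State the postdose window over which peaks and nadirs are taken, for blood pressure as well as pulse, and whether it includes the night on each recording day.

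The cost is one more derived variable, with its change from baseline, from data already recorded. No measurement, visit or clinical rule changes.
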